Study Title: Accelerated Genital Tract Aging in HIV: Estradiol Clinical Trial

NCT04079218

IRB Number: 2019-10529

Accelerated genital tract aging in HIV: estradiol clinical trial

1. Background

HIV is associated with accelerated and accentuated aging as evidenced by *earlier onset* and *increased prevalence* of several age-related conditions including cardiovascular, neurocognitive and bone disease¹⁻⁴. Chronic HIV infection and aging may be linked by a common mechanism: inflammation⁵, which is fueled by ongoing low-level viral replication, microbial translocation, immunosenescence, immune activation and ART use⁶. However, the link between HIV infection and genital tract aging in women is understudied and has important clinical implications. The phenotype of female genital tract (FGT) aging is characterized by vaginal dysbiosis (increase in diverse anaerobes and decrease in acid-producing lactobacilli) and mucosal inflammation. These changes are associated with an increased risk for urinary tract and sexually transmitted infections (STI), vaginal atrophy, HIV acquisition and shedding^{7,8,9}. Among incident US HIV infections in 2015, 17% occurred in persons >50 years of age. Approximately 45% of people living with HIV in the US are aged ≥ 50 ^{10,11}, and by 2030 an estimated 70% will be over age 50, underscoring the importance of studying the effects of aging on the FGT and genital health as well as HIV acquisition and shedding.

This proposal will test the hypothesis that HIV is associated with earlier onset and more pronounced changes in the FGT characterized by vaginal dysbiosis and mucosal inflammation. I propose a cross-sectional study to compare a phenotype of FGT aging in HIV-infected (HIV+) and HIV-uninfected (HIV-) menopausal women aged 45-70 years and predict that younger HIV+ menopausal women (45-55 years) will have a phenotype similar to older (56-70 years) HIV-menopausal women. I will also explore whether topical estradiol therapy in HIV+ women with vaginal atrophy will improve symptoms and the age-related phenotype of dysbiosis and inflammation. Results of these studies have important clinical implications and could lead to recommendations for earlier and/or more aggressive treatment of vaginal atrophy in HIV+ women.

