Women with HIV infection experience menopausal symptoms at an earlier age and are more likely to report symptoms compared to women who do not have HIV. Participants may benefit from study participation because the use of low dose topical estradiol, which has been FDA approved since 2009 for the treatment of vaginal atrophy in menopausal women, may relieve symptoms of vaginal dryness, itching, soreness, pain and urinary symptoms in women with HIV. Participants and others may benefit in the future from information learned from this study. Specifically, if we find that HIV accelerates genital tract aging, this may prompt recommendations for earlier treatment of vaginal atrophy in menopausal women with HIV.

10. Data analysis and sample size:

Aim 1: The primary exposure variables are HIV infection and age. The primary outcome is the vaginal microbiome, specifically the relative abundance and quantities of lactobacillus species as measured by illumina MiSeq and qPCR respectively. Secondary outcomes are relative abundance and quantities of specific BV associated bacteria and quantities of CVL cytokine/chemokines. Exploratory outcomes are quantities and composition of Ig coated bacteria and levels of HIV-1 in the genital tract. Multivariate linear regression will be applied for our analysis. General form of the linear regression model will be: $y_i = \mu + \beta_{age_i} + \gamma_{HIV_i} + \theta_{age_i \times HIV_i} + \delta_i \text{Covariates}_i + \dots + \epsilon_i$, in which y_i is the outcome variables subject to necessary transformation as necessary. Age will be analyzed as a continuous variable to examine the slope or rate of change in lactobacillus and as

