a dichotomous variable (e.g. age 45-55 vs. 56-70) to examine the magnitude of difference between younger and older HIV+ and HIV- menopausal participants. We have chosen the age cut offs above given the significant differences observed in the taxonomic composition of the microbiome in pilot studies when comparing HIV+ menopausal participants in these age ranges and the distribution of eligible participants in WIHS. We will adjust the regression analysis for important covariates including years since menopause, time since HIV diagnosis, HIV plasma viral load, CD4 count, ART use, and HSV-2 serostatus. Both raw p values and the false discovery rate (FDR) according to Benjamini and Hochberg will be examined. To limit the false positive rate in our analysis of secondary outcomes, an arbitrary cutoff of 0.05 for FDR will be used.

Power Considerations: We estimated the power of the proposed study using software PASS (Power and Sample Size Analysis, version 11). Given the sample size of 50 HIV- and 50 HIV+ menopausal participants, we will have >80% power for the minimal detectable difference of 0.6SD and 0.9SD between HIV (or age) group with the significance level of 0.05 and 0.0005 (a conservative Bonferroni correction for 100 independent tests). Data from preliminary studies in our lab investigating the impact of menopause and HIV status on the vaginal microbiome indicated 51 HIV+ menopausal participants had a significantly lower relative abundance of lactobacillus species of 7.3% compared to 23% for 19 HIV- menopausal participants, equivalent to about 0.8SD change. Further when comparing upper and lower age ranges of HIV+ menopausal participants, HIV+ participants age 56-70 (n=28) had significantly lower relative proportions of *L. iners* 7.4% compared to 44.7% in HIV+ menopausal participants aged 47-55.9 (n=23), equivalent to about 1.2SD change. Based on the preliminary data, we are confident that this study will have excellent power to detect effects of age and HIV.

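### Do the Aim 1 pilot figures, 7.3% for lactobacillus species but 24.2% pooled for *L. iners* alone in HIV+ women, undermine the power statement?

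*Combined protocol and SAP*

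**What the plan says.** Section 10 of the combined protocol and SAP defines the Aim 1 primary outcome as the vaginal microbiome, "specifically the relative abundance and quantities of lactobacillus species", with no species excluded.

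The power paragraph takes 50 HIV+ and 50 HIV- women as given. It states more than 80% power for a "minimal detectable difference of 0.6SD and 0.9SD between HIV (or age) group", at significance levels 0.05 and 0.0005 respectively.

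Pilot results follow as support, introduced as "Data from preliminary studies in our lab investigating the impact of menopause and HIV status on the vaginal microbiome". There are two contrasts:

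- **HIV:** "51 HIV+ menopausal participants had a significantly lower relative abundance of lactobacillus species of 7.3% compared to 23% for 19 HIV- menopausal participants", put at about 0.8 SD.
- **Age, within HIV+ women:** this one concerns *L. iners* only. The 28 women in the older band are put at "7.4% compared to 44.7% in HIV+ menopausal participants aged 47-55.9 (n=23), equivalent to about 1.2SD change".

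The paragraph ends: "we are confident that this study will have excellent power to detect effects of age and HIV". It gives no SD, summary statistic, denominator or list of included species for either contrast.

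**The concern.** *L. iners* is a lactobacillus. The two age groups add up to the 51 HIV+ women of the HIV contrast, their age bands adjoin, and the text names no new source between the two sentences. The natural reading is one set of women described twice. On that reading the single species averages 24.2% while all lactobacillus species together average 7.3%, which is impossible for means on one denominator.

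HIV is a primary exposure in Aim 1, and 0.8 SD is the only numerical HIV effect offered for the claim of excellent power. If the 7.3% were wrong and the true total were at least 24.2%, HIV+ women would no longer lie below the 23% reported for HIV- women. The pilot support for an HIV effect would then be gone.

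**Working it through.** **Inputs.** All come from section 10, Aim 1, Power Considerations: 7.3% (n = 51) and 23% (n = 19) with 0.8 SD; 7.4% (n = 28) and 44.7% (n = 23) with 1.2 SD; 50 per group; significance levels 0.05 and 0.0005. Sidedness is not stated, so two-sided is assumed.

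**1. The plan's own power figures.** Two-sample t-test, 50 v 50, exact noncentral t:

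| Level | Power at stated difference | Difference detectable at 80% |
|---|---|---|
| 0.05 | 84.4% at 0.6 SD | 0.566 SD |
| 0.0005 | 81.1% at 0.9 SD | 0.892 SD |

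Both statements are reproduced. The pilot percentages do not enter the calculation. Because it is in SD units, it does not depend on which taxa are counted or which denominator is used.

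**2. The pooled species figure.** (28 × 7.4 + 23 × 44.7)/51 = (207.2 + 1028.1)/51 = 1235.3/51 = 24.2%. With rounding of the inputs, the range is (28 × 7.35 + 23 × 44.65)/51 = 24.17 to (28 × 7.45 + 23 × 44.75)/51 = 24.27. The gap from the printed genus figure is 24.2 − 7.3 = 16.9 points. The younger women alone contribute 23 × 44.7/51 = 20.2 points, so the conflict does not depend on the older group.

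**3. Does each contrast hold together on its own?** With t = d × √(n₁n₂/(n₁ + n₂)):

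- HIV: 0.8 × √(51 × 19/70) = 2.98 on 68 df, p = 0.004.
- Age: 1.2 × √(28 × 23/51) = 4.26 on 49 df, p = 0.00009.

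Each stated effect agrees with the plan's description of that contrast as significant. The conflict is between the contrasts, not within either.

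**4. Readings that would reconcile them.**

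- *L. iners left out of the 7.3%.* The Background describes genital aging as an "increase in diverse anaerobes and decrease in acid-producing lactobacilli". The protective species named there and under Aim 2 in section 10 are *L. crispatus*, *L. jensenii* and *L. gasseri*, without *L. iners*. The two sets of figures would then measure different things and could not conflict.
- *All medians.* At least 14 of the 28 older women and 12 of the 23 younger women would be at or above 7.4% for *L. iners*. That is 26 of 51, and the median is the 26th value, so the genus median must be at least 7.4%. Against 7.3% printed, the gap shrinks from 16.9 points to 0.1, about rounding.
- *Species means with a genus median.* Suppose 25 older women are at 0 and 3 at 69.07% (mean 7.4%), and 1 younger woman is at 0 and 22 at 46.73% (mean 44.7%). Then 26 of 51 have no *L. iners*, its pooled median is 0, and a genus median of 7.3% is possible.
- *Another denominator or other women.* *L. iners* could be a share of lactobacilli rather than of all bacteria. The text also speaks of preliminary studies in the plural. Section 4 ties the age cut-offs to a published study, so the age contrast may have its own source, though section 10 does not say so.

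The documents do not choose between these readings or rule out a misprint.

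**The case for a change.** The case for a change is that none of these explanations is printed, that the reader is asked to accept excellent power on the strength of the figures, and that the repair would cost a few sentences. At face value 0.8 SD gives 97.7% power (50 v 50, two-sided 0.05), so the confidence rests on a number nobody can check. If *L. iners* was left out, the 0.8 SD also belongs to a narrower measure than the primary outcome in section 10.

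Much of this stands. The inconsistency is real, and 0.8 SD cannot be derived from what is printed. The doubt is also wider than the HIV effect: because the faulty figure, if there is one, cannot be located, the 1.2 SD age contrast is no better verified.

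Two parts do not carry. The vanishing HIV difference is one branch only. It sets an *L. iners*-inclusive 24.2% against a 23% that would presumably also leave out *L. iners* if the 7.3% does; and if the 7.3% is only a misprint, the 0.8 SD may still come from correct data. Second, the natural replacement for the pilot argument is the detectable difference, and the same paragraph already prints it.

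**Conclusion.** No change to the plan is called for. The pilot figures are inconsistent by 16.9 points if they are means on a common denominator in the same 51 women. They are consistent, or nearly so, under several ordinary readings that the text leaves open. This is a gap in the reporting of background data, not a demonstrated error in a design calculation.

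The sample size was not derived from the pilot effects. The formal power statement holds without them (0.566 and 0.892 SD at 80% power, against 0.6 and 0.9 printed), assuming a two-sided two-sample t-test with 50 per group. The primary outcome, regression model, visits and eventual conclusions are the same whichever pilot figure is right. Rechecking the pilot would at most alter how confident one adjective sounds. A reader who wants a safe statement of Aim 1 power should use the printed detectable differences and treat 0.8 SD and 1.2 SD as unverified background.

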estradiol will improve vaginal symptoms and modify the genital tract aging phenotype. HIV+ women who agree to participate in the trial will have 3 additional study visits: randomization (Visit 3), 6 weeks after randomization (Visit 4) and 12 weeks after randomization (Visit 5). HIV- women can only participate in Aim 1 and will have 2 study visits. HIV+ women can elect to participate in Aim 1 and/or Aim 2 (2 study visits if only Aim 1 is completed; 4 study visits if only Aim 2 is completed; 5 visits if both Aims 1 and 2 are completed).

Inclusion criteria for Aim 1 (first 2 study visits):

- HIV infection or HIV negative
- Females aged 45-70
- Menopause defined by having no menstrual periods for 12 consecutive months, confirmed with serum follicle-stimulating hormone (FSH) level >40 IU/ml and serum estradiol level <20 pg/ml

In the second part of the study (Aim 2), we propose a pilot randomized clinical trial nested in the Bronx WIHS in 50 menopausal WLWH with symptomatic vaginal atrophy to assess the impact of 12 weeks of a topical low-dose estradiol vaginal tablet (Vagifem® 10 µg) on symptoms of atrophy and measures of the vaginal microbiome. Participants will be randomized 1:1 to estradiol (n=25) or no therapy (n=25) and will be followed for 12 weeks. The dosing of Vagifem® will be 1 tablet inserted using a plastic applicator (similar to a tampon) in the vagina daily for 2 weeks followed by 1 tablet inserted twice weekly (i.e., Tuesday and Friday). If we find benefit among women assigned to the estradiol arm, participants randomized to the no therapy arm will be offered vaginal estradiol treatment at the end of the study by their primary care doctor. If participants assigned to Vagifem are symptomatic beyond the 12-week study period and wish to continue Vagifem®, it can be prescribed by their primary care physician. Women will have 3 visits before (Visits 1, 2 and 3) and 2 visits following Vagifem® treatment (Visits 4 and 5). Adherence to Vagifem will be assessed with the use of participant diaries of Vagifem use and counting of used Vagifem applicators.

Inclusion criteria for Aim 2 (randomized clinical trial for HIV+ participants only):

- HIV infection
- Females aged 45-70
- Menopause defined by having no menstrual periods for 12 consecutive months, confirmed with serum follicle-stimulating hormone (FSH) level >40 IU/ml and serum estradiol level <20 pg/ml

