Aim 2: The primary outcomes are clinical symptoms measured by most bothersome symptom of vaginal atrophy and changes in the vaginal microbiome, specifically the relative abundance of protective lactobacillus species *L. crispatus* as measured by Illumina MiSeq and quantities of protective lactobacilli species (*L. crispatus*, *L. jensenii* and *L. gasseri*) as measured by qPCR between baseline and 6 and 12 weeks within individual participants and between participants randomized to estradiol vs. no drug at baseline, 6 and 12 weeks. The 12-week time frame was chosen as this was the endpoint utilized in several clinical trials demonstrating Vagifem efficacy and is recommended in FDA guidelines^{22,43}. The secondary outcomes are changes relative abundance and quantities of specific BV associated bacteria and levels CVL cytokine/chemokines between baseline, 6 and 12 weeks. Exploratory outcomes are the quantities and composition of Ig coated bacteria and levels of HIV-1 in the genital tract. Spearman's correlation coefficients (SCC) will be calculated to evaluate associations between pairs of quantitative outcome variables and covariates, such as levels of protective lactobacilli species and MBS of atrophy, quantity of Ig coated bacteria, inflammatory mediators, CVL HIV-1 RNA, levels of estradiol in the blood. Linear mixed effects models or generalized linear mixed models will be used to examine effects of time and estradiol use on outcomes (bacterial communities, vaginal bacterial quantities, symptoms) after adjustment for factors such as ART, duration of HIV, plasma viral load, and CD4+ T cell count. We will also address the variability of the microbiome and inflammatory mediators over time in the absence of an intervention by comparing these measures at the screening (Visit 2) and enrollment visits (Visit 3).

Power Considerations: We have increased our sample size and added randomization for this clinical trial based on feedback from the NIH reviewers. If we assume an attrition rate of 15%, a sample of 50 HIV+ women randomized to estradiol (Vagifem) vs. no treatment will have >80%

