power for the minimal detectable difference in lactobacilli of 0.85 SD and 1.4 SD with the significance level of 0.05 and 0.0005 (a conservative Bonferroni correction for 100 independent tests), respectively, at 12 weeks post treatment. Although data is lacking in HIV+ women treated with Vagifem, a previous study with a smaller sample size (30 HIV-) investigating the use of low dose (0.3mg) oral conjugated estrogens for treatment of vaginal atrophy in demonstrated a significant increase in the relative abundance of Lactobacillus from 11.2% to 71% ($p<0.0001$) comparing baseline to 4 weeks estrogen treatment. Further the vaginal symptom score decreased from 3.93 vs. 1.00 ($p<0.0001$) at the same time points⁴¹, suggesting this proposed study may have adequate power for detecting a realistic difference of candidate Lactobacillus and symptom score. It should be noted that this is a pilot study and as such we acknowledge that it may be underpowered for testing interaction effects of time and estradiol use. However, the goal of the study is to determine an effect size of topical estradiol in planning for a future large-scale randomized controlled trial.

References

4. Wing EJ. HIV and aging. *International journal of infectious diseases : IJID : official publication of the International Society for Infectious Diseases*. 2016;53:61-68.

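### The Aim 2 primary definition lists before-after changes and between-arm comparisons together, does not single out the week 12 between-arm contrast that the plan powers, and ties baseline to no visit

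*Combined protocol and SAP*

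**What the plan says.** Section 10, Aim 2, names the most bothersome symptom and protective lactobacilli (*L. crispatus* by MiSeq; three species by qPCR) as primary. That makes three to five variables, depending on whether the qPCR species are pooled, which is not stated. They are compared "between baseline and 6 and 12 weeks within individual participants and between participants randomized to estradiol vs. no drug at baseline, 6 and 12 weeks".

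Next comes a reason for the length of follow-up: "The 12-week time frame was chosen as this was the endpoint utilized in several clinical trials demonstrating Vagifem efficacy". The model sentence reads "Linear mixed effects models or generalized linear mixed models will be used to examine effects of time and estradiol use on outcomes", with adjustment for HIV-related factors. No coefficient or contrast is identified as the primary result.

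The power paragraph assumes 50 women and 15% attrition and claims more than 80% "power for the minimal detectable difference in lactobacilli of 0.85 SD and 1.4 SD", at levels 0.05 and 0.0005, for estradiol versus no treatment at 12 weeks. It then cites a study of oral estrogen in women without HIV, "comparing baseline to 4 weeks estrogen treatment", as reason to think power may be adequate. It closes by saying that "the goal of the study is to determine an effect size of topical estradiol in planning for a future large-scale randomized controlled trial".

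On timing, Section 4 counts weeks 6 and 12 from randomisation at Visit 3. Section 6 and Table 1 have symptoms scored before treatment at Visits 2 and 3, and swabs taken at Visits 1, 2 and 3. Section 10 calls Visit 2 screening and Visit 3 enrollment; neither is called baseline.

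**The concern.** The primary sentence joins two different quantities. A within-participant change in treated women is the drug effect plus anything that would have happened without treatment. A between-arm difference removes that shared part, and it is the only one of the two that uses the randomisation. The sentence also includes a between-arm comparison at baseline, which cannot measure a treatment effect.

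Because nothing is ranked, the headline effect size could be chosen after the data are seen: before-after or between-arm, week 6 or week 12, measured from Visit 2 or from Visit 3. For a study whose purpose is to hand an effect size to a later randomised trial, that choice is the main deliverable. Sections 4 and 7 also attach an end-of-study offer to a finding of benefit without saying which result that means.

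**Working it through.** **1. Which contrast does the power figure describe?** Inputs from Section 10: 50 women, 15% attrition, 0.85 SD, level 0.05 (two-sided assumed; sidedness is not stated). Evaluable: 50 × 0.85 = 42.5, or 21.25 per arm.
- Normal approximation: power = Φ(d√(n/2) − 1.96). With n = 21.25, 0.85 × √10.625 = 2.77, giving 79.1%. With n = 22, 80.5%.
- Two-sample t-test: 76.7% with 21 per arm, 78.7% with 22.

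So the stated figure is reproduced, marginally, as one between-arm test at one time point. It is not a figure for a before-after change or for a set of contrasts.

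**2. What a within-arm test does when the drug does nothing.** Assumed: both arms improve by the same Δ; retest correlation r; 21 women in the arm. Paired t-test, 20 df, noncentrality Δ√21 / √(2(1−r)).
- Smallest case: 0.2 × 4.583 / √1.4 = 0.77.
- Largest case: 0.4 × 4.583 / √0.6 = 2.37.

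| Shared change | r = 0.3 | r = 0.5 | r = 0.7 |
|---|---|---|---|
| 0.2 SD | 11% | 14% | 20% |
| 0.3 SD | 20% | 26% | 39% |
| 0.4 SD | 31% | 41% | 61% |

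The between-arm test has a true difference of zero in every cell, so it rejects in 5%. Both rates are for two-sided tests.

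**3. Consequence if a later trial were sized on the before-after change.** Assumed: 80% power, two-sided 0.05, t-test, both effects on the raw-score SD scale. Example at 0.8 SD: 26 per arm.
- A quarter of the change also occurs untreated: true difference 0.75 × 0.8 = 0.6 SD; noncentrality 0.6 × √13 = 2.16; power 56%. The trial would need 45 per arm.
- Half occurs untreated: 0.4 SD; noncentrality 0.4 × √13 = 1.44; power 29%. It would need 100 per arm.

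Starting from 0.6 or 1.0 SD (45 or 17 per arm) gives the same 56% and 29%.

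**4. Precision of a single week 12 contrast.** 95% half-width with 21 per arm: t(0.975, 40) × √(2/21) = 2.021 × 0.3086 = 0.62 SD. With baseline adjustment, multiply by √(1−r²): 0.60 SD at r = 0.3 and 0.45 SD at r = 0.7 (correlations assumed).

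**The case against.** The strongest reply is that the plan points to the right contrast. The week 12 between-arm comparison is in the primary list, the following sentence justifies 12 weeks, and the power paragraph is built on it. That stands, so a reader who inferred that the plan leaves this contrast out would be wrong; it is present but not singled out. The sentence might also be read as the between-arm difference in change, since the plan mentions the interaction of time and estradiol use. But a between-arm comparison at baseline does not fit that reading, and the plan says that it may be underpowered for that interaction.

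Second, a reader might infer that the plan substitutes the cited before-after result for a between-arm effect when it sets power. The text does not support this: the 0.85 SD is not derived from that study, and the citation is hedged. It shows only how easily the two kinds of effect size sit side by side.

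Third, a reader might infer that multiplicity was ignored. It was not: the power paragraph gives a 0.0005 level, described as Bonferroni for 100 tests. That is a power scenario, however, not a decision rule for the primary outcomes. The FDR cutoff in Section 10 stands in the Aim 1 text and names secondary outcomes only.

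Fourth, changes would be seen in both arms, and the plan compares Visits 2 and 3 to gauge variability without intervention. Both help interpretation. The Visit 2 to 3 comparison covers the microbiome and inflammatory mediators, not symptoms, and neither feature says which number is the result.

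Finally, this is a pilot. That softens the testing issue, but an estimation goal makes the choice of estimate matter more.

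**Conclusion.** The point holds as a defect of definition. The power arithmetic is reproduced within rounding and the randomised design is sound. What is missing is one designated contrast, the model term that gives it, and a named baseline visit. Visit 3 is the natural baseline because weeks are counted from it, but the plan does not say so.

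The size depends on assumptions that the documents cannot supply. With a shared improvement of 0.2 to 0.4 SD and retest correlation 0.3 to 0.7, a within-arm test credits an inert drug in 11 to 61% of trials, against 5% between arms. A reader might infer that the next trial will therefore be too small. The documents do not show that. It follows only if that trial is sized on the before-after change and untreated women also improve; under those two conditions its power is 56% (a quarter of the change shared) or 29% (half shared) instead of 80%.

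The plan should be changed before analysis.

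**What to change.** In Section 10, Aim 2:
- For each primary outcome, make the estradiol versus no-treatment difference at week 12, adjusted for the Visit 3 value, the primary contrast, and state that Visit 3 is baseline.
- Name the mixed-model term that estimates it, and report the estimate with a 95% confidence interval.
- Move week 6 and within-arm changes to secondary. Describe baseline by arm without treating it as an outcome comparison.
- State which lactobacillus measure the power statement refers to.
- If significance is to be claimed on more than one primary outcome, prespecify how 0.05 is shared.
- Say which result the references to benefit in Sections 4 and 7 mean. The investigators should reconcile those passages with Section 10.

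The cost is wording only: Visit 3 swabs and symptom scores are already scheduled, and the sample size does not change. The downside is that the imprecision becomes visible: about ±0.62 SD unadjusted, or ±0.45 to 0.60 SD with baseline adjustment under the correlations assumed above. If 0.05 were split equally between two outcomes, unadjusted power at 0.85 SD with 21 per arm would fall from about 77% to 66%, and the difference detectable with 80% power would rise from 0.89 to 0.98 SD.

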The study is nested in Bronx WIHS, which is an NIH-funded prospective observational cohort study of HIV+ and at-risk HIV- women. We have identified 90 HIV- and 248 HIV+ Bronx and Brooklyn WIHS participants who are potentially eligible for this study. Potential participants will be invited to discuss this study at semiannual Core WIHS visits. We will recruit participants from the Bronx and Brooklyn WIHS for this study. Bronx WIHS staff will call potentially eligible participants and schedule them to come in to the Clinical Research Center at the Albert Einstein College of Medicine or the Bronx WIHS site for a screening visit. As we have done for prior studies, Brooklyn WIHS participants who are interested in participating in the study, will be contacted by the Bronx WIHS staff and seen at the Bronx WIHS site for all visits. Additional participants may be recruited

from Montefiore Medical center, and may be identified using the Center for AIDS Research Clinical Database.

6. Study procedures

Study visits will occur at the Einstein Clinical Research Center or the Bronx WIHS clinical study site. The study clinicians or study coordinator will screen participants for eligibility, discuss the study, answer any questions, and obtain written informed consent. At each scheduled research visit, a pelvic examination will be performed for the collection of the following specimens: vaginal swabs for pH, and microbiome studies; CVL; vaginal swabs to assess for infection (Visits 1 and 2 only) and vaginal biopsies and a vaginal scraping (VMI) to assess for vaginal aging at (Visits 2 and 5 only) (**Table 1**). If candida, BV, or trichomonas is diagnosed, participants will be notified and referred to their primary doctor for treatment prior to enrollment in the study. After treatment, participants may return for repeat testing and if the infection has resolved, they may be enrolled in the study.

At Visit 2 blood will be collected for estradiol and follicular stimulating hormone (FSH) levels, aging biomarkers and future studies and for HIV positive participants, CD4 and HIV-1 RNA. At Visit 5, blood will be collected for aging biomarkers and future studies. Participants will be asked at Visits 2-5 to complete a questionnaire about the presence and severity of the most bothersome symptom of atrophy, defined as vulvovaginal itching, pain, dryness, irritation or pain with penetration (dyspareunia)⁴³.

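### The Aim 2 mixed model does not require the outcome's own pre-randomisation value to be used; requiring it would be a cheap gain in precision

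*Combined protocol and SAP*

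**What the plan says.** The Aim 2 model is given in one sentence of section 10: "Linear mixed effects models or generalized linear mixed models will be used to examine effects of time and estradiol use on outcomes", "after adjustment for factors such as ART, duration of HIV, plasma viral load, and CD4+ T cell count". The outcome's own starting value is not on that list, and nothing is said about whether the arms share a baseline mean.

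The primary outcomes are the most bothersome symptom and protective lactobacilli. They are to be compared "within individual participants and between participants randomized to estradiol vs. no drug at baseline, 6 and 12 weeks". Visits 2 and 3 receive an explicit analytic role only in describing variability without intervention.

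The power paragraph assumes 50 women and 15% attrition, and claims more than 80% "power for the minimal detectable difference in lactobacilli of 0.85 SD and 1.4 SD" at week 12, at significance levels of 0.05 and 0.0005. It concedes that "it may be underpowered for testing interaction effects of time and estradiol use", and adds that "the goal of the study is to determine an effect size of topical estradiol" for planning a larger trial.

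Section 4 places randomisation at Visit 3, before treatment, with Visits 4 and 5 at 6 and 12 weeks. Table 1 schedules the symptom questionnaire, swabs and lavage at Visits 2 to 5, so the pre-randomisation values will exist.

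**The concern.** The pilot's main product is an effect size, so interval width matters more than usual. The wording permits several mixed models that differ in how much they use baseline. Comparing the arms at baseline as well as at 6 and 12 weeks, and speaking of a time-by-estradiol interaction, both fit an arm-by-visit model in which each arm has its own baseline mean. In that model, with complete data, the week 12 arm difference is the plain unadjusted one and the week 12 interaction is the difference in change scores. Neither uses the correlation between baseline and follow-up efficiently. With about 21 women per arm, precision that is already paid for could be left unused, depending on a coding choice made later.

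**Working it through.** **Inputs.** From the documents: 25 per arm, 15% attrition, 0.85 SD at 0.05 and 1.4 SD at 0.0005, time point week 12. Completers per arm: 25 × 0.85 = 21.25, taken as 21 (N = 42). Assumed: two-sided tests, a linear scale, equal variances, and a baseline to week 12 correlation ρ, which the documents do not give. It is shown over a range.

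**The plan's own figure.** Two independent means, no baseline term:

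| Per arm | 0.85 SD at 0.05: normal / t | 1.4 SD at 0.0005: normal / t |
|---|---|---|
| 21 | 78.7% / 76.7% | 85.5% / 76.2% |
| 22 | 80.5% / 78.7% | 87.8% / 79.6% |

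The claim of more than 80% is reproduced to within about 2 points, except by the t calculation at 21 per arm, which falls 3 to 4 points short. It is therefore consistent with an unadjusted week 12 comparison.

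**Variance of the week 12 estimate (SD = 1, n = 21 per arm).**

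- Unadjusted: 2/n, so SE = √(2/21) = 0.309, with 40 df.
- Change score or interaction: 2(1 − ρ) × 2/n, with 40 df.
- Baseline-adjusted: (1 − ρ²)(39/38) × 2/n, with 39 df. The factor 39/38 allows for chance imbalance at baseline.

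**Break-even points (on variance).**

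- Adjusted against unadjusted: (1 − ρ²)(39/38) = 1 gives ρ = √(1/39) = 0.160. With four further covariates in the model it is √(1/35) = 0.169, where ρ is the partial correlation.
- Adjusted against interaction: 2(1 − ρ) = (1 − ρ²)(39/38) gives ρ = 76/39 − 1 = 0.949.

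So the 0.16 threshold belongs only to the contrast that ignores baseline. The interaction is less precise than the adjusted estimate below 0.16 as well.

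**95% CI half-width (SD).**

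| ρ | Unadjusted | Interaction | Adjusted |
|---|---|---|---|
| 0 | 0.62 | 0.88 | 0.63 |
| 0.3 | 0.62 | 0.74 | 0.60 |
| 0.5 | 0.62 | 0.62 | 0.55 |
| 0.7 | 0.62 | 0.48 | 0.45 |

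**Power at 0.85 SD (noncentral t).**

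| ρ | Unadjusted | Interaction | Adjusted |
|---|---|---|---|
| 0.3 | 76.7% | 62.2% | 79.4% |
| 0.5 | 76.7% | 76.7% | 86.5% |
| 0.7 | 76.7% | 93.4% | 96.0% |

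**In women.** 21 / [(1 − ρ²)(39/38)] gives 22.5 / 27.3 / 40.1 unadjusted women per arm at ρ = 0.3 / 0.5 / 0.7.

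**Checks.** A simulation of 60,000 trials per ρ gave SEs at ρ = 0.5 of 0.271 adjusted and 0.308 unadjusted; at ρ = 0.16 both were 0.309. A three-visit generalised least squares calculation (compound symmetry, 25 per arm, 4 per arm lost during follow-up) gave SEs at ρ = 0.5 of 0.266 with a common baseline mean, and 0.301 for both the free-baseline week 12 difference and the interaction. Dropout does not change the conclusion.

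**The case against.** **The text allows the efficient analysis.** The covariate list is open, so baseline could be added. If estradiol use is coded by visit, as zero for everyone at Visit 3, the arms already share a baseline mean. This stands: the gain is not lost on every reading. But the text leaves it to a later choice.

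**The gain may be small.** The power statement concerns the week 12 difference. Against that contrast, adjustment at ρ = 0.3 moves the half-width only from 0.62 to 0.60 SD and power from 76.7% to 79.4%. This also stands. A reader might infer that the pilot will deliver ±0.74 SD, the interaction figure at ρ = 0.3. The documents do not support that: they raise the interaction only to say that the study may be underpowered for it.

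**The formulas are only a guide for the actual outcomes.** Entry largely requires moderate or severe symptoms on a 0–3 scale, which narrows the baseline range. Section 10 reports 7.3% lactobacillus abundance in HIV+ menopausal women in preliminary data, so *L. crispatus* may sit near its floor at baseline. Either could lower ρ, and a floor could also break equal variances. This stands.

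**Two stronger readings are not supported.** A reader might infer that the model dilutes the treatment effect by averaging in the baseline visit. That needs one constant arm term with baseline kept as an outcome row, whereas the plan compares the arms visit by visit and contemplates an interaction. A reader might also infer that post-randomisation CD4 and viral load will be covariates, because the pooled blood row in Table 1 is marked at Visits 2 and 5. Nothing says so. Section 6 places those tests at Visit 2 and says of the last visit only that "At Visit 5, blood will be collected for aging biomarkers and future studies". The database-extraction row of Table 1, which lists CD4 and plasma HIV-1 RNA, is marked at Visits 1 and 2.

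**Conclusion.** The point holds as a cheap improvement. The plan does not require efficient use of the pre-randomisation value, and the contrasts it names fit a model that would not use it. The consequence is precision and pre-specification, not bias: under randomisation all three week 12 contrasts estimate the same effect on the linear scale.

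The size depends wholly on a correlation that the documents do not give. Against the unadjusted week 12 difference the gain is nil below about 0.16, small at 0.3, and worth roughly 6 women per arm at 0.5 (27.3 against 21). Against the interaction it is larger at low correlations and vanishes near 0.95. These figures assume 42 completers, equal variances and a linear scale, and may overstate the gain for the symptom score and for *L. crispatus*.

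**What to change.** State in section 10 (Aim 2) that the estradiol versus no-therapy differences at weeks 6 and 12 will be estimated from one model with visit and arm-by-visit terms, week 12 being the time point of the power statement. The model should do one of two things:

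- constrain the two arms to a common pre-randomisation mean; or
- enter the Visit 3 outcome value as a covariate, with Visits 4 and 5 as the outcome rows.

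The mean of Visits 2 and 3 may serve as the baseline value where both are collected. Under compound symmetry at ρ = 0.5 the variance factor, before the degree-of-freedom correction, is 1 − 2ρ²/(1 + ρ) = 0.67, against 1 − ρ² = 0.75 for Visit 3 alone. The choice should be named in advance.

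The cost is wording and one degree of freedom; no new measurement is needed. If the correlation were zero, the CI half-width would go from 0.624 to 0.632 SD, about 1%. In a generalized linear mixed model with a non-linear link, the covariate also makes the effect conditional on baseline, and the plan should say so.
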